9.4. Reporting of Serious Adverse Events

Regardless of suspected causality (eg, relationship to study drug or study procedure[s]), all SAEs occurring after the participant has signed the ICF through 30 days after the last dose of study drug *or* until the participant starts a new anticancer therapy, whichever occurs earlier, must be reported to the sponsor (or designee) immediately, without undue delay but not later than within **24 hours** of obtaining knowledge of its occurrence unless otherwise specified by the Protocol. The investigator will submit any updated SAE data to the sponsor (or designee) immediately, without undue delay but not later than within 24 hours of it being available. For Japan, this information must also be reported immediately to the head of the study site.

Investigators are not obligated to actively seek SAE information after 30 days after the last dose of study drug. If the investigator learns of any SAE, including death, at any time during the survival period and he/she considers the event to be reasonably related to the study drug or study participation, then the investigator must notify the sponsor (or designee) within 24 hours of becoming aware of the event.

After the initial AE/SAE report, the investigator is required to proactively follow each participant at subsequent visits/contacts. All SAEs will be followed until resolution, stabilization, the event is otherwise explained, or the participant is lost to follow-up (as defined in Section 7.3).

Prompt notification by the investigator to the sponsor regarding an SAE is essential so that legal obligations and ethical responsibilities toward the safety of participants and the safety of a study drug under clinical investigation are met.

If the SAE is not documented in the RSI of the **IB** for the study drug (new occurrence) and is thought to be related to the study drug, the sponsor or its designee may urgently require further

information from the investigator for expedited reporting to health authorities. The sponsor or its designee may need to issue an Investigator Notification to inform all investigators involved in any study with the same drug that this SAE has been reported. Suspected unexpected serious adverse reactions will be collected and reported to the competent authorities and relevant ethics committees in accordance with Directive 2001/20/EC or as per national regulatory requirements in participating countries.

For Japan, the sponsor will report suspected expected deaths and life-threatening events to the PMDA as per local regulatory requirements.

The sponsor has a legal responsibility to notify both the local regulatory authority and other regulatory agencies about the safety of a study drug under clinical investigation. The sponsor will comply with country-specific regulatory requirements relating to safety reporting to the regulatory authority, IRB/IEC, and investigators.

Investigator safety reports must be prepared for suspected unexpected serious adverse reactions according to local regulatory requirements and sponsor policy and forwarded to investigators as necessary.

An investigator who receives an investigator safety report describing an SAE or other specific safety information (eg, summary or listing of SAEs) from the sponsor will review and then file it along with the IB and will notify the IRB/IEC, if appropriate, according to local requirements.

Serious Adverse Event Reporting

- Information about all SAEs is collected and recorded on the Adverse Event Form in the eCRF.
- The investigator must report within 24 hours of learning of its occurrence any SAE via the EDC system (primary method) or by completing the Serious Adverse Event Report Form in English (only if the EDC system is not available. The contact information for Incyte Pharmacovigilance by email/fax is listed in the Study Reference Manual or as per the Incyte Reference Guide for Completing the Serious Adverse Event Report Form).
- In circumstances where the EDC system is not accessible for reporting SAE information (initial and/or follow-up SAE information) to the sponsor within 24 hours, refer to the Incyte Reference Guide for Completing the Serious Adverse Report Form. Once the EDC system is functional, the SAE report should be retrospectively added to the EDC system and follow-up should be completed through the EDC. The original copy of the Serious Adverse Event Report Form and the email or facsimile confirmation sheet must be kept at the study site (refer to the Incyte Reference Guide for Completing the Serious Adverse Report Form or Study Reference Manual for details and for the email address or fax number).
- Follow-up information is also recorded in the eCRF and transmitted to Incyte Pharmacovigilance via the EDC system. The follow-up report should include information that was not provided previously, such as the outcome of the event, treatment provided, action taken with study drug because of the SAE (eg, dose reduced, interrupted, or discontinued), or participant disposition (eg, continued or withdrew from study participation). Each recurrence, complication, or progression of the original event should be reported as follow-up to that event, regardless of when it occurs.

9.5. Events of Clinical Interest

Not applicable.

9.6. Emergency Unblinding of Treatment Assignment

Not applicable.

9.7. Pregnancy

Pregnancy, in and of itself, is not regarded as an AE unless there is suspicion that the study drug may have interfered with the effectiveness of a contraceptive medication or method. When a pregnancy has been confirmed in a participant during maternal or paternal exposure to study drug, the following procedures should be followed in order to ensure safety:

- The study drug must be interrupted immediately (female participants only).
- If the female participant is no longer pregnant and meets the treatment continuation criteria within 28 days of the scheduled start of a cycle, study treatment may be resumed after approval has been received from the sponsor medical monitor.
- The investigator must complete and submit the Incyte Clinical Trial Pregnancy Form to the sponsor or its designee within **24 hours** of learning of the pregnancy.

Data on fetal outcome are collected for regulatory reporting and drug safety evaluation. Follow-up should be conducted for each pregnancy to determine outcome, including spontaneous or voluntary termination, details of the birth, and the presence or absence of any birth defects, congenital abnormalities, or maternal and/or newborn complications, by following until the first well-baby visit. Pregnancy should be recorded on a Clinical Trial Pregnancy Form and reported by the investigator to the sponsor or its designee. Pregnancy follow-up information should be recorded on the same form and should include an assessment of the possible causal relationship to the sponsor's study drug to any pregnancy outcome, as well as follow-up to the first well-baby visit or the duration specified in local regulations, whichever is later. Refer to the Incyte Reference Guide for Completing the Clinical Trial Pregnancy Form or Study Reference Manual.

Any SAE occurring during pregnancy of a study participant must be recorded on the Serious Adverse Event Report Form and submitted to the sponsor or its designee.

Abnormal pregnancy outcomes (eg, spontaneous abortion, fetal death, stillbirth, congenital anomalies, or ectopic pregnancy) are considered SAEs (if occurring in the study participant) and must be reported as described in Section 9.4. If an abnormal pregnancy outcome is reported in a study participant's partner, the event should be reported to the sponsor on the Clinical Trial Pregnancy Form.

9.8. Warnings and Precautions

Special warnings or precautions for the study drug, derived from safety information collected by the sponsor or its designee, are presented in the [IB](#). Additional safety information collected between IB updates will be communicated in the form of Investigator Notifications. Any important new safety information should be discussed with the participant during the study as necessary. If new significant risks are identified, they will be added to the ICF.

9.9. Product Complaints

The sponsor collects product complaints on study drugs and drug delivery systems used in clinical studies in order to ensure the safety of study participants, monitor quality, and facilitate process and product improvements.

All product complaints associated with material packaged, labeled, and released by the sponsor or its designee will be reported to the sponsor. All product complaints associated with other study material will be reported directly to the respective manufacturer.

The investigator or his/her designee is responsible for reporting a complete description of the product complaint via email or other written communication to the sponsor contact or respective manufacturer as noted in the packaging information. Any AE associated with a product complaint should be recorded as described in Section 9.3.

If the investigator is asked to return the product for investigation, he/she will return a copy of the product complaint communication with the product.

For Japan: Complaints associated with unapproved medical devices will be reported to the sponsor with a Medical Device Defect Report Form, and the sponsor will report medical device defects to the PMDA as per local regulatory requirements.

9.10. Treatment of Overdose

There has been no clinical experience with overdose of pemigatinib. Treatment of overdose should consist of general supportive measures.

10. STATISTICS

10.1. Sample Size Determination

The patient population selected for this trial includes participants with recurrent GBM or other gliomas, circumscribed astrocytic gliomas, and glioneuronal and neuronal tumors with an activating FGFR1-3 mutation or fusion/rearrangement. For these participants, there is no defined standard of care. Second surgery or reirradiation are options for select participants. Alkylating chemotherapy such as nitrosoureas or TMZ rechallenge, as well as the VEGF antibody bevacizumab are alternative options. Response rates reported in randomized trials with chemotherapy in recurrent GBM have been less than 20% (Seystahl et al 2016). Approximately 82 participants each are planned for the final analysis of the primary endpoint of ORR in Cohort A. Cohort assignment is based on central genomic laboratory results. With the assumed rate of 28% for pemigatinib, a sample size of approximately 82 participants would provide about 80% probability to have a 95% CI with lower limit of > 15%. Up to 82 participants will be enrolled in Cohort B, which will provide an approximately 80% chance of observing at least 20 responders in this cohort if the underlying ORR is 28%.

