10.2. Populations for Analysis

The populations for analysis are provided in [Table 15](#).

Table 15: Populations for Analysis

| Population | Description |
|-------------------|--|
| Full analysis set | 
The full analysis set includes all enrolled participants who received at least 1 dose of pemigatinib in Cohorts A and B.
 
The full analysis set will be used for the summary of demographics, baseline characteristics, participant disposition, and analyses of all efficacy data.
 |
| Safety | 
The safety population includes all enrolled participants who received at least 1 dose of pemigatinib.
 
All safety analyses will be conducted using the safety population.
 |
| Per protocol | Participants in the full analysis set who are considered to be sufficiently compliant with the Protocol compose the per protocol population. |
| RANO evaluable | 
The RANO evaluable population includes all participants in the full analysis set who have at least 2 postbaseline objective tumor response assessments per ICR or who withdraw from the study or discontinue from treatment without post-treatment tumor assessments.
 
The RANO evaluable population will be used for ORR analysis in the interim analysis.
 |

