10.5. Interim Analysis

As limited efficacy data are available for pemigatinib in GBM, a futility analysis will be performed for Cohort A when approximately 25 participants are enrolled into this cohort and have at least 2 postbaseline objective tumor response assessments per ICR or are withdrawn from the study or discontinued from treatment without post-treatment tumor assessments. Cohort A can be closed for futility if ≤ 4 responders are observed in the RANO evaluable population, for which there is $< 5\%$ probability of claiming ORR $> 15\%$ at final analysis. Given the small sample size at the interim analysis and the possible confounding factors, this rule is for internal guidance and is nonbinding. The totality of data collected, including responders as well as participants with SD, will be taken into account in the decision to continue or terminate Cohort A.

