3.3. Sample Size Considerations

The patient population selected for this trial includes participants with recurrent GBM or other gliomas, circumscribed astrocytic gliomas, and glioneuronal and neuronal tumors with an activating FGFR1-3 mutation or fusion/rearrangement. For these participants, there is no defined standard of care. Second surgery or reirradiation are options for selected participants. Alkylating chemotherapy, such as nitrosoureas or temozolomide rechallenge, as well as the vascular endothelial growth factor antibody bevacizumab, are alternative options. Response rates reported in randomized trials with chemotherapy in recurrent GBM have been less than 20% (Seystahl et al 2016). Approximately 82 participants are planned for the final analysis of the primary endpoint of ORR in Cohort A. With the assumed rate of 28% for pemigatinib, a sample size of approximately 82 participants would provide about 80% probability to have a 95% CI

with lower limit of > 15%. Up to 82 participants will be enrolled in Cohort B, which will provide an approximately 80% chance of observing at least 20 responders in this cohort if the underlying ORR is 28%.

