5.3.3. RANO-Evaluable Population

The RANO-evaluable population will include all participants in the FAS who completed a baseline scan and have at least 1 of the following criteria:

- ≥ 2 postbaseline objective tumor response assessments per ICR
- Withdrawn from the study
- Discontinued treatment without post-treatment follow-up tumor assessment

The RANO-evaluable population will be used for ORR analysis at the interim analysis.

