7.2. Analysis of the Primary Efficacy Parameters

7.2.1. Primary Efficacy Analysis

The primary endpoint of the study is ORR in Cohort A. Objective response rate is defined as the proportion of participants who achieve a BOR of CR or PR, based on RANO ([Wen et al 2010](#)), as assessed by an independent centralized radiological review committee. Confirmation of CR and PR is required and documented in the Independent Central Review Charter. This primary analysis of ORR will be based on the FAS. Participants who do not have sufficient baseline or on-study response assessment information to be adequately assessed for response status will be included in the denominators in the calculation of ORR. The 95% CI for the ORR will be estimated using the Clopper-Pearson method.

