9. INTERIM ANALYSES

As limited efficacy data are available for pemigatinib in GBM, a futility analysis will be performed for Cohort A when approximately 25 participants are enrolled into this cohort and have at least 2 postbaseline objective tumor response assessments per ICR or are withdrawn from the study or discontinued from treatment without post-treatment tumor assessments. Cohort A can be closed for futility if ≤ 4 responders are observed in the RANO-evaluable population, for which there is $< 5\%$ probability of claiming ORR $> 15\%$ at final analysis. Given the small sample size at the interim analysis and the possible confounding factors, this rule is for internal guidance and is nonbinding. The totality of data collected, including responders, as well as participants with SD, will be taken into account in the decision to continue or terminate Cohort A.

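### The stated 80% chance of success for Cohort A leaves out the futility look; if that rule is followed at 25 participants, it is about 74% at an ORR of 28%

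*Protocol*

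**What the plan says.** Protocol 10.1 justifies the size of Cohort A by stating that "a sample size of approximately 82 participants would provide about 80% probability to have a 95% CI with lower limit of > 15" (percent), with an assumed ORR of 28%. SAP 3.3 repeats it: "With the assumed rate of 28% for pemigatinib, a sample size of approximately 82 participants would provide about 80% probability". Neither section mentions an interim look.

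Protocol 10.5 plans one: "Cohort A can be closed for futility if ≤ 4 responders are observed in the RANO evaluable population". It takes place at about 25 participants. SAP 9 has the same rule: "Cohort A can be closed for futility if ≤ 4 responders are observed in the RANO-evaluable population". Both attach a probability below 5% of claiming an ORR above 15% at the end. Both add that "this rule is for internal guidance and is nonbinding" (the words are the Protocol's) and that all the data, including stable disease, will inform the decision.

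The look uses the RANO-evaluable set. In Protocol 10.2 this takes in those "who have at least 2 postbaseline objective tumor response assessments per ICR or who withdraw from the study", or who stop treatment without later tumor assessments. SAP 5.3.3 confirms that "The RANO-evaluable population will be used for ORR analysis at the interim analysis". For the primary endpoint, SAP 7.2.1 adds: "Confirmation of CR and PR is required and documented in the Independent Central Review Charter".

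**The concern.** A futility rule lowers the chance of success whenever it is acted on, because some cohorts that start slowly would have recovered. Leaving the rule nonbinding keeps the false-positive chance safe if it is ignored, but does nothing for the chance of success if it is obeyed. The plan gives a probability of success that excludes the look, and one property of the rule (below 5%). It does not give the chance of closing Cohort A when the drug works as assumed, or the chance of success with the rule in use.

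The people deciding on closure therefore see a reassuring figure below 5% and a stated 80%, and could conclude that following the rule costs almost nothing. Protocol Table 2 records that there is no data monitoring committee.

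**Working it through.** **Inputs.** N = 82, assumed ORR 28%, and a target that the lower 95% limit exceeds 15% (Protocol 10.1, SAP 3.3). Clopper-Pearson interval, with non-assessable participants kept in the denominator (Protocol 10.4.1, SAP 7.2.1). Look at about 25, closing at 4 or fewer responders (Protocol 10.5, SAP 9). The 25 are treated as an ordinary sample of the 82, with independent responses at a common rate.

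**1. The plan's own figure.** The Clopper-Pearson lower limit is 14.56% at 19/82 and 15.58% at 20/82, so success means at least 20 responders.

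P(X82 ≥ 20 | 0.28) = 0.8012. This reproduces the stated 80% with no look in the calculation.

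**2. With the rule followed at 25, all eventual responders counted.**

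P(success) = Σ (x = 5 to 25) P(X25 = x) × P(X57 ≥ 20 − x), where 57 = 82 − 25.

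| True ORR | Success, no look | Success, rule followed | P(close) = P(X25 ≤ 4) |
|---|---|---|---|
| 28% | 80.12% | 73.81% | 13.04% |
| 15% | 1.72% | 1.45% | 68.21% |

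The loss at 28% is 80.12 − 73.81 = 6.31 percentage points. The share of closed cohorts that would have reached 20/82 is (0.8012 − 0.7381) / 0.1304 = 0.484.

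**3. The figure below 5%.** With exactly 4/25, success needs 16 of the remaining 57. At the observed rate, 4/25 = 16%, P(X57 ≥ 16 | 0.16) = 1.5%, which agrees with the plan. At the design rate, P(X57 ≥ 16 | 0.28) = 54.5%. The plan's statement is sound at the observed rate, but does not say that this is the rate it assumes.

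**4. Interim size.** Both documents say approximately 25. With the same threshold at an ORR of 28%:

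| Interim n | Success | P(close) |
|---|---|---|
| 23 | 70.1% | 18.6% |
| 24 | 72.1% | 15.6% |
| 25 | 73.8% | 13.0% |
| 28 | 77.2% | 7.4% |
| 30 | 78.5% | 5.0% |

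**5. Responses not yet countable.** Scans are every 9 weeks, and a confirmatory scan comes at least 4 weeks after the previous one (Protocol 8.2.1). A continuing participant enters the interim set with two postbaseline assessments, so a response first seen at the second scan can still be unconfirmed at the look. The documents do not say how often this would happen. As an illustration only, suppose each eventual responder among the 25 is countable with probability q, independently. The interim count is then Binomial(25, 0.28q):

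| q (assumed) | Success at ORR 28% | P(close) at ORR 28% |
|---|---|---|
| 1.00 | 73.8% | 13.0% |
| 0.95 | 71.4% | 16.6% |
| 0.90 | 68.4% | 20.7% |
| 0.80 | 60.5% | 31.1% |

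**The case against.** The strongest reply is that nothing stated is miscalculated. The 80% refers to a sample of about 82, and a cohort closed at 25 lies outside that statement. The rule is openly discretionary, so 73.8% describes a mechanical policy to which the sponsor has not committed. Under the stated policy, with a look at 25 and all responders counted, success lies between 73.8% and 80.1%, depending on how often the rule is overridden. SAP 3.2 calls all analyses exploratory, and SAP 7.1 states no efficacy hypotheses. An interim at 30 would cut the loss to under 2 points.

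Much of this stands. The 80% is correct as a fixed-sample figure, and 74% must be presented as conditional. The size of the effect of late responses is not established: the values of q are assumed, the Independent Central Review Charter is not available here, and Protocol 10.5 and SAP 9 speak of responders without saying whether they must be confirmed. A response at the first scan can be confirmed by the second. The set also admits people who leave early without two assessments, so it may not be an ordinary sample of the 82, and 73.8% is approximate for that reason too.

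It does not remove the point. The rule is there to inform closure, interim sizes of 24 to 28 still give 72.1% to 77.2%, and the sponsor chose to justify the sample size by a probability of success.

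**Conclusion.** The concern holds. At an ORR of 28%, the probability of success is 80.1% if the futility rule is not acted on and 73.8% if it is followed at 25, a loss of 6.3 points. The probability of closing Cohort A is 13.0% at an ORR of 28% and 68.2% at 15%. These figures assume that the 25 are representative of the 82 and that every eventual responder among them is counted at the look. Responders not yet countable can only move success down and closure up; by how much is unknown.

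The consequence is limited. The final estimate and its interval are unaffected, the false-positive chance is slightly lower with the rule than without it, and the statement of a probability below 5% is not an error. It should be corrected because it concerns the primary endpoint and the decision to close its cohort.

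**What to change.** In Protocol 10.1 and SAP 3.3, state that the probability of about 80% applies if the futility rule is not acted on, and is about 74% if it is followed at 25 participants with every eventual responder among them already counted, and lower if responses are late or unconfirmed.

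In Protocol 10.5 and SAP 9, give the stopping probabilities under the same assumption: about 13% at an ORR of 28% and about 68% at 15%. The sponsor can substitute its own figures if it assumes something different about the RANO-evaluable interim set.

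Two optional additions would help: the range over interim sizes of 24 to 28 (about 72% to 77%), and the response rate assumed behind the figure below 5%.

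The cost is wording in four sections. The bound, the sample size and the confidence interval method do not change.
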